5.5 Criteria for Taking a Participant Off Protocol Therapy

Duration of therapy will depend on individual response, evidence of disease progression and tolerance. In the absence of treatment delays due to adverse event(s), treatment may continue for 12 cycles or until one of the following criteria applies:

- Disease progression
- Intercurrent illness that prevents further administration of treatment
- Unacceptable adverse event(s)
- Participant demonstrates an inability or unwillingness to comply with the oral medication regimen and/or documentation requirements

- Participant decides to withdraw from the protocol therapy
- General or specific changes in the participant's condition render the participant unacceptable for further treatment in the judgment of the treating investigator
- Recurrent toxicity (see section 6)
- Patient becomes pregnant or cannot comply with birth control requirements.

Participants will be removed from the protocol therapy when any of these criteria apply. The reason for removal from protocol therapy, and the date the participant was removed, must be documented in the case report form (CRF). Alternative care options will be discussed with the participant.

A QACT Treatment Ended/Off Study Form will be filled out when a participant is removed from protocol therapy. This form can be found on the QACT website or obtained from the QACT registration staff.

In the event of unusual or life-threatening complications, treating investigators must immediately notify the Overall PI, [name] at [contact] or [contact] ([name]).

5.6 **Duration of Follow Up**

Participants will be followed for 3 years from the initiation of treatment, until subsequent therapy or until removal from study or death, whichever occurs first. Participants removed from protocol therapy for unacceptable adverse event(s) will be followed until resolution or stabilization of the adverse event.

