5.7 Criteria for Taking a Participant Off Study

Participants will be removed from study when any of the following criteria apply:

- Lost to follow-up
- Withdrawal of consent for data submission
- Initiation of subsequent therapy
- Death
- Completion of all study procedures

The reason for taking a participant off study, and the date the participant was removed, must be documented in the case report form (CRF).

A QACT Treatment Ended/Off Study Form will be filled out when a participant comes off study. This form can be found on the QACT website or obtained from the QACT registration staff.

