6. DOSING DELAYS/DOSE MODIFICATIONS

Dose delays and modifications will be made as indicated in the following table(s). The descriptions and grading scales found in the revised NCI Common Terminology Criteria for Adverse Events (CTCAE) version 4.03 will be utilized for dose delays and dose modifications and version 3.0 should be used for tumor flare. A copy of the CTCAE version 4.0 can be downloaded from the CTEP website

http://ctep.cancer.gov/protocolDevelopment/electronic applications/ctc.htm.

Note that tumor flare reaction is managed differently from other AEs as outlined in Table 4. Lenalidomide should be held for any grade 3 or higher toxicity except in the incidence of a blistering skin rash, in which case lenalidomide should be permanently discontinued though patients will be followed for resolution of toxicity and for survival. In the event of a blistering skin rash the patient should have an urgent dermatology referral if grade 1 or 2 and should be hospitalized if grade 3 or 4. If a patient develops venous thromboembolism and/or pulmonary embolism while on therapeutic anticoagulation lenalidomide treatment should be permanently discontinued regardless of grade unless anticoagulation dosing was low (e.g., INR or anti-factor Xa was not in the generally accepted therapeutic range). Patients experiencing a venous thromboembolic event while on aspirin alone may stay on protocol at the discretion of the treating physician as long as the patient is subsequently on systemic anticoagulation with warfarin, low molecular weight heparin or equivalent for the duration of the study and as clinically indicated thereafter by the nature and extent of the thrombotic event. Patients experiencing an arterial thromboembolic event will be removed from study regardless of the anticoagulation status at the time of the event.

Per table 2, participants may be dose reduced if toxicities occur during cycle 1 at the starting dose of 10 mg daily. No more than 2 dose reductions will be permitted. If the participant cannot tolerate therapy after 2 dose reductions they should be permanently removed from the protocol.

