Grade 4	 and reduce the dose of lenalidomide by 1 dose level at the start of the next cycle. Omitted doses are not made up. If Grade 4, discontinue lenalidomide. Remove patient from study.
Venous thrombosis/embolism ≥ Grade 3	 Hold (interrupt) lenalidomide and start therapeutic anticoagulation, if appropriate. If VTE occurs while patient is on therapeutic anti-coagulation (not counting aspirin) permanently discontinue treatment. Restart lenalidomide at investigator's discretion (maintain dose level). See Anticoagulation Consideration (Section 5.6.1.2)
Hyperthyroidism or hypothyroidism	 Omit lenalidomide for remainder of cycle, evaluate etiology, and initiate appropriate therapy. See Instructions for Initiation of a New Cycle and reduce the dose of lenalidomide by 1 dose level.
Other non- hematologic toxicity ≥ Grade 3	 Hold (interrupt) lenalidomide dose. Follow at least weekly. If the toxicity resolves to ≤ grade 2 prior to Day 21 of the current cycle, restart lenalidomide and continue through the scheduled Day 21 of the current cycle. Otherwise, omit for remainder of cycle. Omitted doses are not made up. For toxicity attributed to lenalidomide, reduce the lenalidomide dose by 1 dose level when restarting lenalidomide.

Table 4. Tumor Flare Reaction Treatment (TFR)

Treatment of TFR is up to the discretion of the investigator, depending upon the severity and clinical situation. It is suggested that Grades 1 and 2 TFR be treated with NSAIDs (i.e., ibuprofen 400 to 600 mg orally every 4 to 6 hours as needed), corticosteroids, and/or narcotic analgesics for pain management.

In mild to moderate (Grades 1 and 2) cases, it is suggested that study drug be continued along with symptomatic treatment as above. In more severe cases, study drug should be interrupted.

Tumor Flare Reaction (TFR) ^a Grades 1-2	 Continue lenalidomide, maintain dose level At the investigator's discretion may initiate therapy with NSAIDs, limited duration corticosteroids, and/or narcotics
Grades 3-4	 Hold (interrupt dose) and initiate therapy with NSAIDs, corticosteroids, and/or narcotics When symptoms resolve to ≤ Grade 1, restart at same dose level for the rest of the Cycle

Treatment of Overdose

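### The Section 6 text and the Table 3 VTE row do not state the permanent-stop rule identically (grade range, low-anticoagulation exception), and the row cites a section that does not exist.

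*Combined protocol and SAP*

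**What the plan says.** Two parts of Section 6 deal with a VTE in a patient already on therapeutic anticoagulation.

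- **Section 6 text.** For an event "while on therapeutic anticoagulation lenalidomide treatment should be permanently discontinued regardless of grade unless anticoagulation dosing was low". Low dosing is illustrated by the case where "INR or anti-factor Xa was not in the generally accepted therapeutic range".
- **Section 6, Table 3 (dose modifications).** The row is headed "Venous thrombosis/embolism ≥ Grade 3". It tells staff to hold the drug and start anticoagulation where suitable, then says: "If VTE occurs while patient is on therapeutic anti-coagulation (not counting aspirin) permanently discontinue treatment". It goes on to leave restarting to the investigator, and closes with "See Anticoagulation Consideration (Section 5.6.1.2").

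Section 6 opens by making its tables the operative source for delays and modifications. It does not say whether text or table prevails where they differ.

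Section 5.6 concerns length of follow-up: "Participants will be followed for 3 years from the initiation of treatment, until subsequent therapy or until removal from study or death, whichever occurs first". The next heading is "5.7 Criteria for Taking a Participant Off Study". Prophylactic anticoagulation is covered in Section 5.4.

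**The concern.** A permanent-stop rule should give the same answer wherever staff look it up. Here the text sets a rule for all grades with one exception, while the table sets it within a row limited to grade 3 and above and gives no such exception. Dose-modification tables are often used on their own in clinic, and this protocol directs staff to them.

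What is at stake is mainly safety. The protocol itself names venous and arterial thrombosis as a known risk of lenalidomide, and the passages decide whether a patient continues the drug after a clot. There is a smaller analytic consequence. Section 13.5 counts the best response during study therapy, so stopping one patient and continuing another in the same situation changes how long each has to respond.

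**Working it through.** No formula or plan figure applies to the main point; the check is a comparison of the passages by type of event.

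| VTE while on anticoagulation other than aspirin | Section 6 text | Table 3 VTE row | Result |
|---|---|---|---|
| Below grade 3, level in range | Permanent stop | Row does not apply | Table silent: **gap** |
| Grade 3 or higher, level in range | Permanent stop | Permanent stop | Agree |
| Grade 3 or higher, level below range | Mandatory permanent stop lifted; the general hold at grade 3 or above still applies | Depends on reading (below) | **Ambiguous** |
| Below grade 3, level below range | Mandatory permanent stop lifted | Row does not apply | No stop required by either |

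**The gap.** No other Table 3 row catches a lower-grade VTE, since the row for other non-hematologic toxicity also begins at grade 3. The table can express an all-grade rule when one is intended: its blistering-rash row does so. Section 5.2.2 allows a new cycle once other drug-related events are at grade 2 or lower. A reader using Table 3 with Section 5.2.2 could therefore restart the drug after a grade 2 event for which the Section 6 text requires a permanent stop.

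**The ambiguity.** The table's mandatory stop depends on the patient being on *therapeutic* anticoagulation.

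1. If that means a measured level in range, a below-range patient does not trigger the stop. Hold and discretionary restart apply, and the table agrees with the text.
2. If it means prescribed treatment-dose anticoagulation, the below-range patient is stopped permanently, and the table differs from the text.

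The text uses the same term and still writes the low-dosing case as an exception to it, which fits reading 2. The table's only stated exclusion is aspirin.

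**The cross-reference.** Section 5.6 has no subsections and is followed directly by 5.7. Both are present in the document, so removed pages or redaction do not explain the absence of 5.6.1.2.

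**Who could be affected.** Sections 3.1.7 and 5.4 make aspirin the default, and the table excludes aspirin from this rule. Those exposed are patients already anticoagulated for another reason, aspirin-intolerant patients given warfarin or low molecular weight heparin, and patients moved to systemic anticoagulation after a first VTE on aspirin. No rate is given for any of these groups.

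**Analytic scale.** With 12 patients (Section 13.1), one patient is 1/12 = 8.3 percentage points of the response rate, and the threshold for further study is 3 of 12. This is the weight of one patient's outcome, not an estimate of bias.

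**The case against.** The strongest reply is that text and table can both be followed. Below grade 3 the table gives no instruction to continue, so the text governs every grade and the table adds hold-and-restart steps from grade 3 upward. On the exception, an ordinary reader may well say that a patient below the therapeutic range is not on therapeutic anticoagulation, so the two passages state one rule in different words. The dead reference may be no more than a wrong section number, since prophylaxis is in Section 5.4 and VTE handling is in the Section 6 text.

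Much of this stands, and it rules out several stronger readings that a reader might infer:

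- *The table orders continuation after a lower-grade VTE.* It does not; it is silent.
- *The exception is a proven conflict.* It is not; one plausible reading removes the difference.
- *The text directs that a patient with low anticoagulation stays on drug.* It only lifts the mandatory permanent stop.
- *The missing section would have settled the matter.* Nothing in the documents shows what it contained.
- *Every VTE with below-range anticoagulation is affected.* Below grade 3 neither passage requires a stop, so only events of grade 3 or higher can differ.

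What the reply does not remove is that the tables are declared operative, no precedence is stated, and the all-grade rule cannot be found from the table.

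**Conclusion.** The point holds as an internal inconsistency of wording in a safety rule. The table omits the permanent stop for VTE below grade 3, it leaves the low-anticoagulation exception unstated and so open to two readings at grade 3 or higher, and its cross-reference leads nowhere. It should be corrected.

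Its size cannot be fixed: the documents give neither a VTE rate nor the number of patients expected to be on non-aspirin anticoagulation, and the group is a subset of 12. The gap rests on staff using the table without the text; the ambiguity rests on how *therapeutic* is understood. The endpoint definition, sample size and analysis set are untouched, and under Section 13.7.2 every patient who takes a dose is still assessed for response.

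**What to change.** Reconcile the Section 6 text with the Table 3 VTE row so that both give the same grade range and state the low-anticoagulation exception, or its absence, in the same words. If the exception stays, say whether therapeutic anticoagulation refers to the prescribed dose or to the measured level. Replace the reference to Section 5.6.1.2 with the section intended, or delete it. Which grade range and which exception apply is for the clinical team to decide.

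The cost is amendment wording, with no change to design, sample size or analysis.

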7. ADVERSE EVENTS: LIST AND REPORTING REQUIREMENTS

Adverse event (AE) monitoring and reporting is a routine part of every clinical trial. The following list of reported and/or potential AEs (Section 7.1) and the characteristics of an observed AE (Section 7.2) will determine whether the event requires expedited reporting in addition to routine reporting.

7.1 Adverse Event List(s) for lenalidomide

The most frequently reported adverse events reported during clinical studies with lenalidomide in oncologic and non-oncologic indications, regardless of presumed relationship to study medication include: anemia, neutropenia, thrombocytopenia and pancytopenia, abdominal pain, nausea, vomiting and diarrhea, dehydration, rash, itching, infections, sepsis, pneumonia, UTI, Upper respiratory infection, atrial fibrillation, congestive heart failure, myocardial infarction,

chest pain, weakness, hypotension, hypercalcemia, hyperglycemia, back pain, bone pain, generalized pain, dizziness, mental status changes, syncope, renal failure, dyspnea, pleural effusion, pulmonary embolism, deep vein thrombosis, CVA, convulsions, dizziness, spinal cord compression, syncope, disease progression, death not specified and fractures.

Second New Cancers

In clinical studies of newly diagnosed multiple myeloma, a higher number of second cancers were reported in patients treated with lenalidomide as induction therapy (treatment for several cycles to reduce number of cancer cells) and/or bone marrow transplant followed by lenalidomide for a long period of time compared to patients treated with induction therapy and/or bone marrow transplant then placebo (a capsule containing no lenalidomide). Patients should make their doctors aware of their medical history and any concerns they may have regarding their own increased risk of other cancers.

Tumor Flare

Tumor flare assessments are conducted in Cycle 1 on Days 1, 8, and 15 (±1 day), and when clinically indicated thereafter. Tumor flare reaction (TFR) is defined in the NCI-CTCAE version 3 as a constellation of signs and symptoms of tumor pain, inflammation of visible tumor, hypercalcemia, diffuse bone pain, and other electrolyte disturbances in direct relation to initiation of therapy (Cancer therapy evaluation program, 2003).

Tumor flare reaction is an adverse effect of lenalidomide previously reported in subjects with CLL (27). In clinical studies of lenalidomide in subjects with non-Hodgkin lymphoma (NHL) (28), TFR has also been reported at a lower rate in NHL patients than in CLL patients (29,30). The onset of TFR has been as early as within a few hours after the first dose of lenalidomide and occurs within the first 2 to 3 weeks of the first Cycle in the vast majority of TFR cases. TFR subsides over time and usually resolves in 1 to 2 weeks with or without intervention (28).

Pregnancy

Lenalidomide is known to be teratogenic thus women of child-bearing potential and men must agree to use adequate contraception as outlined in the REMS® program. Pregnancies and suspected pregnancies (including a positive pregnancy test regardless of age or disease state) of a female subject occurring while the subject is on lenalidomide, or within 28 days of the subject's last dose of lenalidomide, are considered immediately reportable events. Lenalidomide is to be discontinued immediately. The pregnancy, suspected pregnancy, or positive pregnancy test must be reported to Celgene Drug Safety immediately by facsimile or email using the Pregnancy Initial Report Form. The female subject should be referred to an obstetrician-gynecologist, preferably one experienced in reproductive toxicity for further evaluation and counseling. The Investigator will follow the female subject until completion of the pregnancy, and must notify Celgene Drug Safety immediately about the outcome of the pregnancy (either normal or abnormal outcome) using the Pregnancy Follow-up Report Form. If the outcome of the pregnancy was abnormal (e.g., spontaneous or therapeutic abortion), the Investigator should report the abnormal outcome as an AE. If the abnormal outcome meets any of the serious criteria, it must be reported as an SAE to Celgene Drug Safety immediately by facsimile, or other appropriate method, within 24 hours of the Investigator's knowledge of the event using the SAE Report Form.

All neonatal deaths that occur within 28 days of birth should be reported, without regard to causality, as SAEs. In addition, any infant death after 28 days that the Investigator suspects is related to the in utero exposure to the IP should also be reported to Celgene Drug Safety immediately by facsimile, or other appropriate method, within 24 hours of the Investigator's knowledge of the event using the SAE Report Form.

Complete and updated adverse events are available in the Investigational Drug Brochure and the IND Safety Letters

7.2 Adverse Event Characteristics

• **CTCAE term (AE description) and grade:** The descriptions and grading scales found in the revised NCI Common Terminology Criteria for Adverse Events (CTCAE) version 4.0 will be utilized for AE reporting. All appropriate treatment areas should have access to a copy of the CTCAE version 4.0. A copy of the CTCAE version 4.0 can be downloaded from the CTEP web site http://ctep.cancer.gov/protocolDevelopment/electronic applications/ctc.htm.

• For expedited reporting purposes only:

- AEs for the agent(s) that are listed above should be reported only if the adverse event varies in nature, intensity or frequency from the expected toxicity information which is provided.
- Other AEs for the protocol that do not require expedited reporting are outlined in the next section (Expedited Adverse Event Reporting) under the sub-heading of Protocol-Specific Expedited Adverse Event Reporting Exclusions.
- **Attribution** of the AE:
 - Definite The AE *is clearly related* to the study treatment.
 - Probable The AE *is likely related* to the study treatment.
 - Possible The AE *may be related* to the study treatment.
 - Unlikely The AE is *doubtfully related* to the study treatment.
 - Unrelated The AE *is clearly NOT related* to the study treatment.

7.3 Expedited Adverse Event Reporting

7.3.1 Investigators **must** report to the Overall PI any serious adverse event (SAE) that occurs after the initial dose of study treatment, during treatment, or within 30 days of the last dose of treatment on the local institutional SAE form.

Expedited Reporting by Investigator to Celgene

Serious adverse events (SAE) are defined above. The investigator must inform Celgene in writing using a Celgene SAE form or MEDWATCH 3500A form of any SAE within 24 hours of being aware of the event. The written report must be completed and supplied to Celgene by facsimile within 24 hours/1 business day. The initial report must be as complete as possible, including an assessment of the causal relationship between the event and the investigational product(s). Information not available at the time of the initial report (e.g., an end date for the adverse event or laboratory values received after the report) must be documented on a follow-up report. A final report to document resolution of the SAE is required. The Celgene tracking number (RV-CL-OTHER-PI-004617) and the institutional protocol number should be included on SAE reports (or on the fax cover letter) sent to Celgene. A copy of the fax transmission confirmation of the SAE report to Celgene should be attached to the SAE and retained with the patient records.

Celgene Drug Safety Contact Information: Celgene Corporation Global Drug Safety and Risk Management [name] [contact] E-mail: [contact]

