The most frequently reported adverse events reported during clinical studies with lenalidomide in oncologic and non-oncologic indications, regardless of presumed relationship to study medication include: anemia, neutropenia, thrombocytopenia and pancytopenia, abdominal pain, nausea, vomiting and diarrhea, dehydration, rash, itching, infections, sepsis, pneumonia, UTI, Upper respiratory infection, atrial fibrillation, congestive heart failure, myocardial infarction, chest pain, weakness, hypotension, hypercalcemia, hyperglycemia, back pain, bone pain, generalized pain, dizziness, mental status changes, syncope, renal failure, dyspnea, pleural effusion, pulmonary embolism, deep vein thrombosis, CVA, convulsions, dizziness, spinal cord compression, syncope, disease progression, death not specified and fractures.

Second New Cancers

[figure not shown]
In clinical studies of newly diagnosed multiple myeloma, a higher number of second cancers were reported in patients treated with lenalidomide as induction therapy and/or bone marrow transplant followed by lenalidomide. This risk seems to be greatest when the duration of lenalidomide therapy exceeded 2 years.

Complete and updated adverse events are available in the Investigational Drug Brochure and the IND Safety Letters.

Lenalidomide Description

Lenalidomide, a thalidomide analogue, is an immunomodulatory agent with anti-angiogenic properties. The chemical name is 3-(4-amino-1-oxo 1,3-dihydro -2*H*-isoindol-2-yl) piperidine-2,6-dione and it has the following chemical structure:

Chemical Structure of Lenalidomide

3-(4-amino-1-oxo 1,3-dihydro-2H-isoindol-2-yl) piperidine-2,6-dione

The empirical formula for lenalidomide is $C_{13}H_{13}N_3O_3$, and the gram molecular weight is 259.3.

Lenalidomide is an off-white to pale-yellow solid powder. It is soluble in organic solvent/water mixtures, and buffered aqueous solvents. Lenalidomide is more soluble in organic solvents and low pH solutions. Solubility was significantly lower in less acidic buffers, ranging from about 0.4 to 0.5 mg/ml. Lenalidomide has an asymmetric carbon atom and can exist as the optically active forms S(-) and R(+), and is produced as a racemic mixture with a net optical rotation of zero.

Clinical Pharmacology

Mechanism of Action:

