7.3.2 DF/HCC Expedited Reporting Guidelines

Investigative sites within DF/HCC and DF/PCC will report SAEs directly to the DFCI Office for Human Research Studies (OHRS) per the DFCI IRB reporting policy.

7.4 Expedited Reporting to Hospital Risk Management.

Participating investigators will report to the Risk Management office any participant safety reports or sentinel events that require reporting according to institutional policy.

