7.5 Routine Adverse Event Reporting

All Adverse Events must be reported in routine study data submissions to the Overall PI on the

toxicity case report forms. AEs reported through expedited processes (e.g., reported to the IRB, FDA, etc.) must also be reported in routine study data submissions.

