13.4 Interim Monitoring Plan

The study will be referred to the DSMC for review of dosing and toxicity at the first occurrence of a toxic death.

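### The only specified toxicity tabulation, 13.6(d), stops at grade 4 and so omits fatal toxicity; a lesser point is that prompt notice to the Overall PI of a late second cancer is unclear

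*Combined protocol and SAP*

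**What the plan says.** **Toxicity analysis.** Section 1.3 sets a secondary objective of describing lenalidomide's safety profile in the three diseases. Section 13.1 lists a description of toxicity among the secondary endpoints, with no grade limit. Section 13.6(d) is the only place that turns this into an analysis: the proportion of participants with grade 3-4 toxicity, for each CTC v4 code. Section 13.7.1 makes everyone who takes one dose evaluable. On monitoring, 13.4 says: "The study will be referred to the DSMC for review of dosing and toxicity at the first occurrence of a toxic death".

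**Reporting window.** Section 7.3.1 obliges investigators to report to the Overall PI any SAE that occurs after the first dose, during treatment, or "within 30 days of the last dose of treatment on the local institutional SAE form". Follow-up lasts 36 months from the start of treatment (sections 1 and 5.6), or less if a new therapy, removal from study or death comes first. Section 7.1 describes second cancers as a risk: in newly diagnosed myeloma, "a higher number of second cancers were reported in patients treated with lenalidomide as induction therapy". Section 2.2 adds: "This risk seems to be greatest when the duration of lenalidomide therapy exceeded 2 years". Section 7.2 says that, for expedited reporting, listed agent events are reported only when they differ from the expected information.

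**Other routes.**
- Section 5.5: "In the event of unusual or life-threatening complications, treating investigators must immediately notify the Overall PI".
- Section 7.3.1, reports to Celgene: the investigator must inform it in writing "of any SAE within 24 hours of being aware of the event", with no end date.
- Section 7.3.2: sites "will report SAEs directly to the DFCI Office for Human Research Studies (OHRS) per the DFCI IRB reporting policy".
- Section 7.5: "All Adverse Events must be reported in routine study data submissions to the Overall PI".
- Section 12.2: the DSMC reviews toxicity up to four times a year, or more often if required.

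**The concern.** The toxicity tabulation excludes the worst grade on the scale it uses. The event that 13.4 treats as serious enough for DSMC referral is one that 13.6(d), taken at its word, does not count. Overall survival and PFS count deaths, but not by cause, so neither shows that a death was due to treatment. A report that followed 13.6(d) exactly could show no severe toxicity under the code from which a patient died.

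The second matter is timing. Second cancers are a delayed risk that the protocol itself describes, yet they have no reporting rule of their own. Pregnancy, by contrast, does have one in 7.1. If 5.5 is not read to reach into follow-up, the Overall PI could learn of a late, non-fatal second cancer only through routine data submission, while other patients are still taking the drug.

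**Working it through.** The plan gives no figure on either matter. Its one statistical figure, the 90% exact interval of 7-53% for 3 responses in 12 (13.1), reproduces as 7.2%-52.7%. It is unaffected by anything here.

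**A. What 13.6(d) counts.** Inputs: 12 patients (13.2), all assumed to receive at least one dose; grade 5 is death due to the event. For a single toxicity code:

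| Event in that code | Grades 3-4 (as written) | Grades 3-5 |
|---|---|---|
| One patient, grade 5 only | 0/12 = 0% | 1/12 = 8.3% |
| One patient grade 4, another grade 5 only | 1/12 = 8.3% | 2/12 = 16.7% |
| One patient, grade 4 then grade 5 | 1/12 if each grade is entered; 0/12 if only the worst grade is | 1/12 = 8.3% either way |

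The third row matters because 13.6(d) does not say whether patients are classified by worst grade. Extending the range to grade 5 removes that ambiguity.

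**B. How much follow-up lies after the 7.3.1 window.** Inputs: 28-day cycles with dosing on days 1-21 and at most 12 cycles (5.1); a delay of at most 28 days before a cycle (5.2.2); a 30-day window (7.3.1); 36 months = 36 × 30.4375 = 1,095.75 days.

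- 12 undelayed cycles: last dose on day 11 × 28 + 21 = 329; window closes on day 359; remainder 1,095.75 − 359 = 736.75 days; 736.75 / 1,095.75 = 67%.
- 12 cycles, each of cycles 2-12 delayed by 28 days: last dose on day 329 + 11 × 28 = 637; window closes on day 667; remainder 428.75 days, or 39%.
- One cycle only: window closes on day 21 + 30 = 51; remainder 1,044.75 days, or 95%.

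Each is an upper bound for its schedule, since follow-up can end early. The share is zero if it ends within 30 days of the last dose. The first follow-up visit is 3 months (91.3 days) ± 14 days after the last dose (section 10, footnote m), so it falls 91.3 − 14 − 30 = 47 to 91.3 + 14 − 30 = 75 days after the window closes. No scheduled follow-up visit lies inside the window; the off-treatment visit does.

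**C. Who might still be exposed.** At 5 patients a year (13.2), entries are 12 / 5 = 2.4 months apart. Treatment lasts at most 329 / 30.44 = 10.8 months without delays. That gives about 10.8 / 2.4 = 4.5 patients on drug at a time once accrual is established. This assumes even accrual and that everyone completes 12 undelayed cycles. Progression and toxicity will lower it.

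**D. How likely such an event is.** The documents give no rate. If each patient had an assumed risk p of a second cancer after the window, the chance of at least one in 12 is 1 − (1 − p)^12: 6% at p = 0.5%, 11% at 1%, 22% at 2% and 46% at 5%. These show only how the answer depends on p. Section 2.2 ties the greatest risk to more than 2 years of therapy, whereas 12 undelayed cycles last 12 × 28 = 336 days, so the upper values have no support in the documents.

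**E. Whether another route gives the Overall PI prompt notice.**
- 5.5 is immediate and has no time limit. But it sits among the off-therapy criteria, does not define what is unusual, and does not name second cancers.
- The Celgene and IRB-office routes do not go to the Overall PI, and the IRB policy is not in the documents.
- 7.5 does reach the Overall PI, but on the routine schedule.
- 13.4 is triggered only by a toxic death.
- The 7.2 filter could be read to remove second cancers from expedited reporting even inside 30 days, because 7.1 describes them.

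**The case against.** On 13.6(d), the endpoint list in 13.1 is not limited by grade, section 12.2 allows the DSMC to be given a summary of deaths within 30 days of intervention, and a toxic death among 12 patients would be hard to leave out of a report. All of that stands. A reader might infer that treatment-related deaths would go unrecorded or unreviewed; the documents do not support that. But 13.1 does not alter the counting rule in 13.6(d), so the tabulation as written remains incomplete.

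On 7.3.1, a reader might infer that a second cancer found after 30 days would go unreported. The documents do not support that either. Celgene must be told of any SAE within 24 hours with no cut-off, the IRB office is told as its policy requires, routine forms reach the Overall PI, and the section 10 calendar marks adverse event evaluation at follow-up. A new cancer can fairly be called an unusual complication under 5.5. Accrual is at a single center (13.1) and the multicenter section (12.3) is marked not applicable, so it is unlikely that a treating investigator would notify Celgene within a day while the Overall PI waited for forms. DSMC review adds a further check. What survives is narrow: the text leaves the timing of notice to one recipient, for one rare event type, to interpretation.

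**Conclusion.** The main point holds on the wording. The only specified toxicity analysis excludes grade 5, contrary to the ungraded objective and endpoint list. Its size is one patient in 12 (8.3 percentage points) per toxic death in the affected code, assuming all 12 are treated and no grade 3-4 entry for that code is counted for the same patient.

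The second point holds only as an ambiguity about prompt notice to the Overall PI of a late, non-fatal second cancer. The 39%-95% of follow-up after the window measures calendar time under full 36-month follow-up; it does not measure harm. The practical effect is small.

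Severity is low: both changes are optional safety improvements. Neither affects the primary endpoint, its decision rule or the sample size.

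**What to change.** In 13.6(d), change grades 3-4 to grades 3-5 and add that any second primary malignancy is listed, whatever its grade.

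In 7.3.1, add one sentence: *Any second primary malignancy is reported as an SAE to the Overall PI and to Celgene from the first dose to the end of study follow-up, regardless of time since last dose, attribution, or the expectedness condition in section 7.2.* The last clause is needed because the 7.2 filter could otherwise exempt an event described in 7.1.

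The cost is a few words and one sentence. No visit is added, since adverse event evaluation is already scheduled in follow-up. The downside is at most a few extra SAE forms in 12 patients.
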